 - Secondary objectives will be to compare group change in UUI episodes at 6 & 12 months, other voiding diary parameters (urinary frequency, pad counts, cure and "durable cure"), and change in the OAB-qSF and other questionnaires (see 1.2) at 2, 6 & 12 months.
- 2. Both a cross sectional study and RCT which will compare pre-treatment brain function in subjects with UUI to controls and compare the effect of hypnotherapy and pharmacotherapy on brain function in patients with UUI.
 - Up to eighty women (of the planned 152) with UUI will be recruited in order to obtain up to sixty analyzable fMRI datasets. Up to 30-35 normative controls will be recruited in order to achieve 25-30 analyzable fMRI datasets from normative controls. fMRI datasets from UUI patients will be compared to fMRI datasets from normative controls. The normative controls will be involved in the study for a month or less.
 - In addition, the same, up to 80, UUI subjects will also undergo fMRI analysis after receiving treatment (hypnotherapy or pharmacotherapy) for two months. Post treatment fMRI results from UUI subjects will be compared to their baseline images. These UUI subjects will complete the fMRI portion of the trial after being "on study" for 2 months but will continue to have follow up for the RCT analysis for one year (See #1 above)
 - Measured outcomes will be differences in baseline brain activation and connectivity in UUI subjects compared to controls as well as differences in treatment effect on brain activation and connectivity in subjects receiving pharmacotherapy compared to those receiving hypnotherapy

1. Study Objectives

1.1 Primary Objective:

- 1.1.1. To determine whether a mind/body therapy (hypnotherapy) is at least as effective and durable in treating urgency urinary incontinence (UUI) as a non-mind/body treatment (pharmacotherapy), comparing between group changes in UUI episodes recorded on voiding diaries at 2 months based on a non-inferiority design.
- 1.1.2. To determine whether hypnotherapy treatment of UUI (urgency urinary incontinence) is associated with greater modification of brain activation and connectivity on functional MRI than that which occurs following pharmacotherapy

1.2 Secondary Objectives:

- 1.2.1 To determine whether a mind/body therapy (hypnotherapy) is at least as effective and durable, in treating urgency urinary incontinence (UUI) as a non-mind/body treatment (pharmacotherapy).

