Primary outcome measures for Objective 2.2 will be pharmacotherapy treated subject versus hypnotherapy treated subject change in task related activation of the insula and anterior cingulate cortex and change in resting functional connectivity between these groups. The test-retest reliability of fMRI results have been evaluated in multiple settings including within multicenter research consortiums.⁸² Assessment of the reliability of brain activation within regions of interest has shown intra-class correlation coefficients frequently greater than 0.8.³⁰ Test-retest reliability has also been shown to be preserved over a one year time span.³

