9.6 Data Analyses

Specific Aim 1: Determine whether a mind/body therapy (hypnotherapy) is as, or is more effective and durable, in treating urgency urinary incontinence (UUI) than a non-mind/body treatment (pharmacotherapy)

Statistical Analysis: Improvement between hypnotherapy and controls will be compared at baseline and followup at 2, 6, 12 months. Because of the possibility that a number of subjects may be cured (i.e. report "0" urgency incontinence episodes) at follow-up on voiding diary, we will use a zero inflated Poisson (ZIP) generalized linear mixed model for the analysis and compare groups' urgency incontinence episodes. The ZIP model analysis is proposed because the data are expected to be relatively low counts with the potential of a large numbers of zeroes, particularly at 2 and 6 months, in excess of those allowed by the Poisson. Simple conversion to percent change will not correct the discrete nature of the data ("cures" become 100 percent change rather than 0 UUI count at 2 months), and standard least squares methods will not be appropriate. If there is no inflation at 0, i.e. standard Poisson regression is appropriate, then the associated log-linear model yields percent change as a natural parameter (by exponentiating the group effect). If there is significant inflation at 0, the confidence interval for percent change in the mean will be constructed by combining the two portions of the model with standard error estimated by the delta method, and checked via bootstrap methods. We will be able to derive mean UUI episodes as well as mean % change in UUI episodes following ZIP model analyses. All other parameters, which are normally distributed or continuous variables, will be compared using a linear mixed model analysis. It is unlikely that there will baseline differences between groups, given that this is a randomized controlled trial. If baseline differences between groups are found (e.g. incontinence duration, coexisting illnesses, prior treatment), appropriate variables will be added to the analysis as covariates. We will include pre-treatment patient expectations and hypnotic susceptibility as covariates in the analysis and determine if they are independent predictors of treatment response. We will not exclude subjects based on hypnotic susceptibility to increase the generalizability of our findings. We anticipate subjects' pre-treatment expectations will be an independent predictor of improvement in urgency incontinence & guestionnaire scores (the previously determined sample size is adequately powered to find a relatively small partial R² of .05¹³ between expectations and outcomes). The primary outcome measure will be change in UUI episodes from baseline to follow-up with a between group comparison, and not "cure". However, the term "cure" may be used for secondary analyses. As such, our definition of "cure" will be: absence of UUI episodes recorded on voiding diaries at 2, 6 and 12 month follow-up. Primary analyses will be performed using intention to treat. A per protocol analysis will also be performed; those who did not comply with the study interventions, extensively used other concomitant treatments known to improve UUI (e.g. used other UUI medications, underwent sacral neuro-modulation), or missed multiple treatment sessions will be considered to have been off protocol subjects. Similar analyses will be performed comparing group differences in change in questionnaire scores while accounting for covariates such as pain/interstitial cystitis (based on VAS pain scale and IC questionnaire) or bowel abnormalities (based on the CRADI-8), medical history and demographic variables (based on the medical history and demographic sheets) on the outcomes.

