Statistical Analysis 2.2 Pre- and Post-Treatment measurements in patients with UUI: Efficacy of hypnotherapy and pharmacotherapy on anterior cingulate cortex and right insula activation will be compared using a 2x2 (Group x Time) mixed model ANCOVA to correct for potential differences in group characteristics (e.g. age). Analysis of treatment effect will be focused on the anterior cingulate cortex and insula based on preliminary data that suggests the effect size for change in activation will be highest in these regions. Prior functional MRI analysis during the hypnotic state has shown complete suppression of anterior cingulate cortex activation in response to pain.⁵⁵ However, the magnitude of suppression of anterior cingulate cortex or insula signal outside the hypnotic state has not been studied. Current study size will be able to detect differences between pre and post treatment signal within a treatment group with an effect size of approximately 0.5 and a power of 0.8. Minimal effect size would be approximately equivalent to a 60% decrease in the excess (above normative control) anterior cingulate cortex and insula signal. We predict a main effect of time, suggesting that both treatments are effective in reducing activity within the anterior cingulate cortex and insula. However, we also predict a significant Group x Time interaction, indicating that that change in activity will be greater for the hypnotherapy relative to the pharmacotherapy group. Minimum detectable effect size for the Group X Time interaction is 0.7 with power of 0.8 and alpha of 0.05. Simple effects tests will also be conducted to ensure that randomization to treatment arm was successful (i.e. no differences in baseline activity across the two groups).

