Similar analyses will be conducted to evaluate the effect of treatment on functional connectivity. No prior data is available in the literature regarding the expected change in waking state connectivity following hypnotherapy. Current study size will be able to detect within-group differences between pre and post treatment signal with a minimal effect size of approximately 0.5 and a power of 0.8, much lower than the observed effect size of >3 in our pilot study. The minimum effect size would be reached with a 15% decrement in anterior cingulate cortex to insula connectivity. As for evoked activity we predict both a main effect of time, and predict a significant Group x Time interaction, indicating that change in functional connectivity will be greater for the hypnotherapy relative to the pharmacotherapy group. Minimum detectable effect size for the Group X Time interaction is 0.7 with power

of 0.8 and alpha of 0.05. This minimum effect size will be reached when between group differences in anterior cingulate cortex to insula connectivity are \geq 30%.

The principal purpose of this analysis will be to explore the mechanism of action of hypnotherapy when used to treat UUI, using pharmacotherapy as a control treatment that is not expected to exert its therapeutic effect via the brain. In addition we will explore the utilization of evoked activity and functional connectivity as biomarkers by correlating changes in these fMRI parameters with physiologic outcome measures, specifically UUI episodes. We understand that there is currently insufficient literature to determine the optimal method of assessing this correlation in the setting of a non-inferiority study design, and will look towards OCRA guidance on this aspect of the analytic plan in the future.

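### Aim 2: the Group x Time test compares raw change scores and does not use each woman's baseline signal as a covariate, a modest and avoidable loss of precision

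*Combined protocol and SAP*

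**What the plan says.** The between-arm difference in change in limbic activation and connectivity is the second primary outcome (Sections 3, 9.1 and 9.5). Section 9.6, Statistical Analysis 2.2, says that activation "will be compared using a 2x2 (Group x Time) mixed model ANCOVA to correct for potential differences in group characteristics (e.g. age"). The effect of interest is the interaction, "indicating that that change in activity will be greater for the hypnotherapy relative to the pharmacotherapy group". The sensitivity claimed for it is: "Minimum detectable effect size for the Group X Time interaction is 0.7 with power of 0.8 and alpha of 0.05". For connectivity, "Similar analyses will be conducted to evaluate the effect of treatment on functional connectivity". Section 9.2 repeats the power statements.

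The pre-treatment scan enters as one of the two response levels. Its only other use is a check on balance: "Simple effects tests will also be conducted to ensure that randomization to treatment arm was successful". No section makes the pre-treatment signal a covariate or holds the arms to a common baseline mean. The missing-data text in Section 9.3 does condition on earlier measurements, but only in a multiple-imputation sensitivity analysis.

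For the Aim 1 questionnaires, Section 9.6 says: "Similar analyses will be performed comparing group differences in change in questionnaire scores". It gives a linear mixed model and an open list of example covariates. It does not say how the baseline score enters.

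**The concern.** The label ANCOVA suggests that baseline is adjusted for. With two time points, however, the Group x Time term subtracts each woman's first scan from her second and compares the mean differences. That fixes the slope on baseline at 1, where regression would estimate it. If the true slope is below 1, subtraction over-corrects for chance baseline differences and adds noise. Age as a main effect does not help, because it is constant within a woman and cancels from her change.

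The planned balance tests do not help either. Under proper randomization any baseline difference is due to chance, and a non-significant result does not remove that difference from the estimate.

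At stake is the precision of a primary outcome that rests on a small subset. Women "with UUI will be recruited in order to obtain up to sixty analyzable fMRI datasets" (Précis), which is at best about 30 per arm.

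**Working it through.** **Inputs from the documents.** Up to 60 analysable datasets (Précis), split about evenly (Section 5.1), so 30 per arm. Detectable interaction effect 0.7, power 0.8, alpha 0.05 (Section 9.6). Test-retest reliability in regions of interest: "intra-class correlation coefficients frequently greater than 0.8" (Section 9.1).

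**Assumptions.** Two-sided alpha and effects in units of the SD of change; the plan states neither. The pre/post correlation under treatment (rho) is not given, nor are the pre- and post-treatment SDs (s1, s2).

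**Step 1: the plan's own figure.** For a comparison of change scores, the detectable effect is (1.96 + 0.84) x sqrt(2/30) = 0.723 by the normal approximation, or 0.736 with the t distribution. Both round to the stated 0.7. At exactly 0.70, power is 77.4% (normal) or 76.0% (t). The within-group claim of about 0.5 also fits: 2.80/sqrt(30) = 0.51.

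**Step 2: Group x Time is the change-score test.** In one simulated dataset of 60 women, fitted with age as a main effect, the interaction was -0.419 (SE 0.167). The difference in mean change was -0.419 (SE 0.167).

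**Step 3: variances per woman.**
- Change score: s1² + s2² - 2·rho·s1·s2
- Baseline-adjusted (large sample): s2²(1 - rho²)
- Difference: s1² - 2·rho·s1·s2 + rho²·s2² = (s1 - rho·s2)²

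The difference is never negative. It is zero when s2 = s1/rho, for example a post/pre SD ratio of 1/0.8 = 1.25 at rho = 0.8. With s1 = s2 the variance ratio is (1 - rho²)/[2(1 - rho)] = (1 + rho)/2.

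**Step 4: size with equal variances, 30 per arm (t-based; 57 error df when adjusted).**

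| Analysis | Variance ratio | Detectable effect | Power at 0.7 |
|---|---|---|---|
| Change score | 1 | 0.736 | 76.0% |
| Adjusted, rho 0.9 | 0.95 | 0.717 | 78.1% |
| Adjusted, rho 0.8 | 0.90 | 0.698 | 80.2% |
| Adjusted, rho 0.7 | 0.85 | 0.678 | 82.4% |
| Adjusted, rho 0.5 | 0.75 | 0.637 | 86.8% |

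In other terms, 60 x 0.90 = 54 women analysed with adjustment match 60 without it at rho 0.8; at rho 0.5 the figure is 60 x 0.75 = 45. Simulation (6,000 runs each) gave power of 76.6% against 79.8% at rho 0.8, and 76.3% against 86.2% at rho 0.5.

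**Step 5: which rho?** The cited reliability is the nearest figure in the documents, but it describes repeatability and not correlation across a treatment. A second clue is indirect. The plan equates an effect of about 0.5 with a 60% fall in excess signal. With the lowest pilot effect size, 0.8, that fall is 0.6 x 0.8 = 0.48 raw SD, so the SD of change is 0.48/0.5 = 0.96 raw SD. Then 2(1 - rho) = 0.92 and rho is about 0.54. With the highest pilot value, 1.5, the same steps give 0.9/0.5 = 1.8, so 2(1 - rho) = 3.24 and rho = -0.62, which is not credible. This clue cannot establish rho, so 0.5 stays an assumption.

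**The case against.** The strongest reply is that the planned test is sound. In a randomized comparison Group x Time is unbiased with correct type I error, and it already subtracts each woman's baseline. Both points stand. A reader might infer that the Aim 2 estimate is biased, or that imbalance is handled only by the balance tests. The documents support neither reading, since those tests come in addition to the subtraction.

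The gain is also small where the documents offer any guide. At rho = 0.8 it is about 4 power points, it shrinks above 0.8, and 0.736 and 0.698 both round to the stated 0.7. A reader might infer that adjustment is always strictly better. It is better or equal in large samples, and the (1+rho)/2 ratio needs equal variances. Varied response to treatment could raise the post-treatment SD and narrow the gain.

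The plan does not say whether age enters as a main effect or is crossed with time. Crossing would alter the interaction, but it would still not adjust for the baseline signal. The covariate list is open, yet the pre-treatment signal is not named and is already used as a response.

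A reader might extend the loss to the Aim 1 questionnaires. The text does not support that. A linear mixed model with a common baseline mean, or with the baseline score as a covariate, would already capture the gain; one with free baseline means would not. Section 9.6 does not say which is meant. It gives no questionnaire correlation, and the one-before, one-after formula does not carry over to several follow-up visits. The point also does not reach the Aim 1 primary outcome, which uses a zero-inflated Poisson mixed model.

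**Conclusion.** The point holds for Aim 2, as a matter of efficiency. The primary between-arm test is a raw change-score comparison, and baseline signal collected for every scanned woman is left out as a covariate. With 30 per arm and equal variances, adjustment lowers the variance by 10% at rho = 0.8 and by 25% at an assumed rho of 0.5. The first is the better-supported case, and it brings power at 0.7 from about 76% to the stated 80%. The direction (variance no larger in large samples) does not depend on the value of rho or on equal variances; the size depends on both, and the documents give neither. For the questionnaires the finding is only that handling of the baseline score is unspecified. The change is worth making because it needs no new data, but the planned analysis would not be invalid without it.

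**What to change.** - **Primary between-arm test.** For each region-of-interest beta and each connectivity measure, regress the post-treatment value on arm and the baseline value, with the UUI-severity randomization stratum and age if desired. An equivalent choice is a mixed model that holds the arms to a common baseline mean; this also keeps the time effect that the plan wants to describe.
- **Balance tests.** Drop the baseline simple-effects tests of whether randomization succeeded. Report baseline values by arm descriptively.
- **Power text.** Restate the detectable-effect sentences in Sections 9.2 and 9.6 for the new analysis, including the equivalent connectivity difference. Give sidedness and the SD used, and label rho and equal variances as assumptions.
- **Questionnaires.** State whether the baseline score is a covariate or a response with a common mean across arms.

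The cost is plan wording and a recalculation of the power statements, with no new scans, visits or data. Section 11.2 notes that enrollment is complete, so the amendment should be dated before the blind is broken.

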*Explanation of age range for the above: In an attempt to assure comparable age ranges of controls to affected UUI subjects, we initially pooled data from both our pilot hypnotherapy and pilot fMRI studies and have found that the median patient age was 54 with the second quartile=46-54, and third quartile=55-62. We initially chose these quartiles as the age range for the normative control group but subsequently found that the age range was overly restrictive in the upper age ranges. We expanded the upper limit to 80 years in order to have flexibility in age adjustment of controls.

Exclusion Criteria for normative controls participating in the fMRI study: Women who have any of the exclusion criteria as specified below will be excluded from participation in the fMRI portion of the study

- Women with UUI/OAB
- Women with a history of neurologic diseases such as Multiple Sclerosis, Parkinson's disease, stroke, or dementia
- History of schizophrenia or untreated bipolar disorder or current drug or alcohol dependence
- Pregnant women or lactating women, women who plan to become pregnant in the next year, or premenopausal women unwilling to use contraception if engaging in sexual relations during the year of study participation (hysterectomy is considered to be a form of contraception)
- Untreated urinary tract infection
- Women with a history of severe claustrophobia or women with ferro-magnetic implants such as cochlear implants, cardiac pacemakers or aneurysm clips

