9.1 General Design Issues

This study includes

- 1. A single-blinded, randomized controlled trial (RCT) based on a non-inferiority design which compares hypnotherapy to pharmacotherapy in treating UUI.
 - Urge incontinent women (N=152) will be randomized to hypnotherapy or pharmacotherapy and evaluated at months 2, 6 &12
- 2. Both a cross sectional study and RCT which will evaluate up to 80 of these women with UUI.
 - These women will undergo fMRI before treatment and their baseline imaging results will be compared to normative controls.
 - In addition, the UUI subjects participating in the fMRI will undergo imaging after treatment. The images of UUI subjects following treatment will be compared to their baseline images.

Specific Aims, Hypotheses and Outcomes;

Primary Outcomes:

- 1. Between group differences in change in UUI episodes for Specific Aim 1 at 2 month follow-up based on 3 day voiding diaries
- 2. Between group differences in change in activation of limbic cortex and brain connectivity following treatment for Specific Aim 2

Secondary Outcomes:

- 1. Between group differences in change in UUI episodes for Specific Aim 1 from baseline to follow-up at both 6 and 12 months based on 3 day voiding diaries.
- Between group differences in change in pad counts, voiding frequency and cure (resolution) of UUI on voiding diary for Specific Aim 1 at 2, 6 and 12 month follow-up as well as "durable cure" (resolution of UUI on all follow-up diaries at 2, 6 & 12 months)
- 3. Between group differences in the follow-up expectation question and between group differences in questionnaire change scores (the OAB-qSF, ISI, PISQ-12, Global questionnaire, CRADI-8, IBS Module, IC questionnaire) for Specific Aim 1 at 2, 6 and 12 month follow-up
- 4. Baseline differences in activation of the limbic cortex and brain connectivity in women with UUI compared to normative controls for Specific Aim 2

1. Specific Aim 1: Determine whether a mind/body therapy (hypnotherapy) is as, or is more effective and durable, in treating urgency urinary incontinence (UUI) than a non-mind/body treatment (pharmacotherapy) Hypothesis: Among patients with urgency urinary incontinence, hypnotherapy ameliorates abnormal perception of bladder distension outside the hypnotic state and thereby diminishes symptoms of urgency and decreases incontinence as effectively as (or more effectively than) pharmacotherapy

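### The age correction planned for the fMRI treatment comparison does not reach the Group x Time test unless age is entered with its time interaction, which the plan does not state (minor)

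*Combined protocol and SAP*

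**What the plan says.** Section 9.6 (Statistical Analysis 2.2) compares hypnotherapy and pharmacotherapy on anterior cingulate and right insula activation by a "2x2 (Group x Time) mixed model ANCOVA to correct for potential differences in group characteristics (e.g. age". Age is the only characteristic named. For connectivity it adds: "Similar analyses will be conducted to evaluate the effect of treatment on functional connectivity".

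Section 9.1 gives the Aim 2 primary outcome as "Between group differences in change in activation of limbic cortex and brain connectivity following treatment for Specific Aim 2". With one scan before and one after treatment, that contrast is the Group x Time term, and 9.6 treats it so: "we also predict a significant Group x Time interaction". The pooled change is also to be interpreted: "We predict a main effect of time, suggesting that both treatments are effective in reducing activity".

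The planning figures are "Minimum detectable effect size for the Group X Time interaction is 0.7 with power of 0.8 and alpha of 0.05" for the interaction and, for pre-post change, detection "within a treatment group with an effect size of approximately 0.5 and a power of 0.8".

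The plan gives no list of model terms. It does not say whether a covariate enters alone or with its time interaction, which other characteristics may be added, or whether women with only one usable scan stay in the model.

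**The concern.** The ANCOVA has a stated purpose, which is to correct the arm comparison for differences in characteristics such as age. That comparison is a difference in change. A characteristic that is fixed within a woman and entered only as a main effect explains differences in level between women, not differences in change within them. On that reading the adjustment is present in the model but has no effect on the primary Aim 2 test.

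Age is a reasonable thing to adjust for here. Randomisation is stratified by fMRI participation and incontinence severity (sections 3 and 9.2), not by age. The Précis plans for up to 60 analysable data sets from up to 80 women, so the analysed arms may differ somewhat from the randomised ones. Leaving the form of the covariate open also leaves a choice that changes the primary estimate to be made when the data are analysed.

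**Working it through.** **Inputs.** Up to 60 analysable women (Précis), about half per arm (section 3), so 30 per arm. Interaction effect size 0.7, power 0.8 and alpha 0.05 (section 9.6); sidedness is not stated, so two-sided is assumed. Any relation between age and change is an assumption, because the documents give none.

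**1. The plan's own figures.** With two time points, Group x Time is a two-sample comparison of change scores.
- Interaction: (1.960 + 0.842) x sqrt(2/30) = 2.802 x 0.258 = 0.72, or 0.74 with the t distribution. This agrees with 0.7 at the one decimal given.
- Within group: 2.802 / sqrt(30) = 0.51, or 0.53 with t. This agrees with about 0.5.

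**2. Algebra.** Let g be arm (0/1), t be time (0/1) and u a woman's own level.
- Age as a main effect: y = a + b·g + c·t + d·g·t + h·age + u + e. Her change is c + d·g + (e1 − e0). The h·age term is in both scans and cancels, so the estimate of d does not depend on it.
- Age with its time interaction: add k·age·t. Her change is c + d·g + k·age + (e1 − e0), and d is now adjusted.
- If k is not zero and its term is left out, the estimate of d, given the ages observed, is off by k x (difference in mean age between arms).

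**3. Numerical illustration.** One simulated data set: 30 per arm, complete pairs, no true treatment effect, an assumed age shift of 0.5 SD between arms and an assumed extra slope of 0.4 per SD of age at the second scan. The models are random-intercept models fitted by REML.

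| Model | Group x Time | SE |
|---|---|---|
| Group, Time, Group x Time | −0.1527 | 0.2488 |
| + age | −0.1527 | 0.2488 |
| + age and age x time | −0.3617 | 0.2455 |

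Regressing change on group and age also gives −0.3617 (SE 0.2455). This shows which models agree. One data set says nothing about bias.

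**4. Incomplete pairs.** A second simulated data set had 40 per arm, 25% of post-treatment scans missing, and women with one scan retained. Group x Time was −0.008 without age, 0.069 with an age main effect, and −0.290 with age x time. Cancellation is no longer exact, but the shift from the main effect is not the intended correction.

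**5. Size over randomisations.** In SD units of change, with an assumed age-change correlation of 0.3:
- SE without adjustment: sqrt(2/30) = 0.258.
- Share due to chance age imbalance: 0.3 x 0.258 = 0.077; its 95% limit is 1.96 x 0.077 = 0.15.
- SE after adjustment: 0.258 x sqrt(1 − 0.09) = 0.246, which is 4.6% smaller before the lost degree of freedom.
- Detectable effect: 0.72 x 0.954 = 0.69.

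**6. Size given an imbalance.** With age imbalance fixed at 0.25 to 0.5 SD and a slope of 0.2 to 0.4 per SD of age (both assumed; 3,000 simulated trials each, no true effect), the unadjusted estimate was off by 0.05 to about 0.20 residual SD of change, and its conditional type I error was 0.05 to 0.09. With age x time the error in the estimate was about 0, and type I error was 0.046 to 0.053.

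**The case against.** Four points can be made for the plan.

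- **No term list is given.** The text neither includes nor excludes age x time, and its stated purpose fits a model that has it. This stands. A reader might infer that the planned ANCOVA is incapable of adjusting the interaction. The documents do not support that, because with age x time in the model the interaction is adjusted. The finding is that the text does not secure the adjustment and that its ordinary additive reading does not deliver it.
- **The arms are randomised.** This also stands. The unadjusted Group x Time is unbiased over randomisations at its nominal error rate. The 0.077 SD in step 5 is part of the existing standard error, not an extra bias, and the error rates in step 6 are conditional on an imbalance that was fixed by assumption.
- **Cancellation is exact only for complete pairs.** This is true, but step 4 shows that keeping women with one scan does not turn the main effect into the intended correction.
- **An age main effect still has a use.** It adjusts comparisons of level, such as the planned check that baseline activity does not differ between arms. That stands, but the check is not the primary Aim 2 test.

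A reader might also infer that the predicted time effect is at risk, since with uncentred age and age x time the time coefficient would refer to age zero. Nothing in the documents says that age will be left uncentred, and no procedure for the group model is named (section 9.5 mentions SAS software only in general). This is a reason to specify centring, not a fault found in the plan. It also could not occur together with the main problem, which arises only when age x time is absent.

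**Conclusion.** The point holds as a minor improvement. With age as a main effect only and complete pairs, the Group x Time estimate is identical with and without age, so the correction that 9.6 intends for activation and connectivity is not made. This part is algebra and needs no assumption about the data.

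The consequence is modest. The primary test stays valid. What is lost is about 5% in standard error if age correlates 0.3 with change, and protection against an age imbalance that arises by chance or through lost scans. For the imbalances and slopes assumed in step 6, that protection is worth 0.05 to 0.20 SD against a detectable effect of about 0.7. The true age-change relation may be weaker or stronger than assumed.

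**What to change.** In section 9.6 (Statistical Analysis 2.2), for both activation and connectivity:

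- list in advance the characteristics to be corrected for, rather than giving age as an example;
- enter each one centred at its sample mean, together with its covariate x time term. With complete pairs this is equivalent to regressing change on group and the centred covariate;
- read the treatment effect from Group x Time in that model, and the main effect of time at mean age;
- state whether women with only one usable scan are kept.

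Whether the baseline signal should itself be a covariate is a separate question that this change does not settle.

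The cost is a few lines of text and one degree of freedom per covariate, which is a reason to keep the list short with about 60 women. No further data or participants are needed.
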